6.3.3 Exclusion Criteria

The exclusion criteria must follow the most recent IFU which may include but are not limited to the following:

- Known intolerance to any of the device components
- Contraindication to dual antiplatelet therapy (DAPT)
- · Lesion in a saphenous vein graft
- Lesion to left internal mammary artery
- Unprotected left main stenosis
- Woman with childbearing potential
- Age < 18y/o
- Concomitant indication to open heart surgery

Inability to provide written informed consent

6.4 Patient Discontinuation

Once registered, each patient shall remain in the registry until completion of the required follow-up period; however, a patient's participation is voluntary and the patient has the right to withdraw at any time without penalty or loss of benefit. Conceivable reasons for discontinuation may include but not be limited to the following:

- Patient voluntary withdrawal
- Patient withdrawal by physician as clinically-indicated
- Patient lost-to-follow-up: If the patient misses two consecutive scheduled follow up time points, and attempts at contacting the patient are unsuccessful, then the patient is considered lost to follow-up.

No additional data is needed and will be recorded from patients once withdrawn from the registry. Patients will not be replaced.

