4.1 Number of Patients to be Registered and Patient Follow-up

The Italian National Registry will enroll a of 1000 patients in approximately 50 sites throughout the Italian territory where Absorb BVS has regulatory approval and is commercially available.

Patients will have clinical follow-up by telephone contact or office visits.

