4.2 Measures Taken to Avoid and Minimize Bias

In order to minimize bias in assessing MACE outcomes, these events will be adjudicated by an independent committee.

4.3 Clinical follow-up plan: 30 days, 6 months, 1 year, and then yearly up to 5 years after the index procedure.

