5. OUTCOMES/ENDPOINTS

Outcomes are as specified below:

- **5.1 Primary**: the cumulative hierarchical incidence of major adverse cardiac events (MACE) defined as: cardiac death, non-fatal target vessel myocardial infarction (MI), or clinically driven target lesion revascularization (TLR);
- **5.2 Secondary endpoints:** All causes mortality, clinically driven TLR, clinically driven target vessel revascularization (TVR), any revascularisation (non TLR, non TVR) and ARC-defined stent thrombosis, at any time point. Any type of angina post procedure measured by means of the Cardio Test, proposed by the ANMCO (Associazione Nazionale Medici Cardiologic Ospedalieri) [21]
- **5.3 Efficacy parameters**: TLR and TVR up to 5-year follow-up.
- **5.4 Safety "patient oriented" parameters:** all cause mortality, any myocardial infarction, Stent thrombosis based on the ARC classification, up to 5-year follow-up. Data on dual antiplatelet therapy use will also be collected and analyzed.

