6.5 Registry Completion

An eCRF registry completion form must be completed when:

- the patient is considered lost-to-follow-up per the above definition or
- the patient withdraws from the registry or
- the investigator withdraws the patient from the registry or
- the patient's follow-up is terminated upon registry follow-up completed (see Section 4.3 for details)

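### Loss to follow-up can be declared as early as month 6 of 60, with no vital-status check required and nothing said about reopening, so late deaths and events may be under-ascertained

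*Protocol*

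**What the plan says.** Section 6.4 opens with the intention that "each patient shall remain in the registry until completion of the required follow-up period". It then gives possible reasons for discontinuation, and loss to follow-up is one of them. The condition has two parts: "If the patient misses two consecutive scheduled follow up time points, and attempts at contacting the patient are unsuccessful". When both are met, "then the patient is considered lost to follow-up". The section ends its account of discontinuation with "No additional data is needed and will be recorded from patients once withdrawn from the registry".

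Section 6.5 lists the events that require a registry completion form in the eCRF. One of them is that "the patient is considered lost-to-follow-up per the above definition or"; withdrawal by the patient and withdrawal by the investigator are separate items.

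The time points are in section 4.3: "30 days, 6 months, 1 year, and then yearly up to 5 years after the index procedure". On the mode of contact, section 4.1 says "Patients will have clinical follow-up by telephone contact or office visits".

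Cardiac death is a component of the primary endpoint (section 5.1). The patient-oriented safety parameters in section 5.4 are "all cause mortality, any myocardial infarction, Stent thrombosis based on the ARC classification, up to 5-year follow-up".

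**The concern.** The rule counts missed time points regardless of how far apart they are. The first two fall within six months of the procedure, so a patient who is silent early can be discontinued before the 1-year point on which the sample size rests, and well before the 5-year horizon of the safety parameters.

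A patient who has died away from the implanting site will miss visits and may not be reachable by telephone, which are the two conditions of the rule. Nothing in sections 6.4 or 6.5 requires the site to find out whether the patient is alive before filing the form. If losses include a disproportionate share of deaths or of events treated elsewhere, the loss is informative. Kaplan-Meier censoring at last contact does not correct for that, and no later analysis plan can recover data that sites were allowed to stop collecting. Mortality, cardiac death and scaffold thrombosis would then tend to be estimated too low, in a registry whose stated objective (section 3) includes long-term clinical performance.

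**Working it through.** **1. The plan's own figure.** Section 9.3 gives a 95% adjusted Wald interval of 3.1% to 5.6% for 42/1000. With z = 1.96 and z² = 3.84:

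- n~ = 1000 + 3.84 = 1003.84
- p~ = (42 + 1.92)/1003.84 = 0.04375
- half-width = 1.96 × √(0.04375 × 0.95625/1003.84) = 0.01265
- interval = 3.11% to 5.64%

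The stated interval is reproduced. It makes no allowance for losses, but precision is not the problem: with 5% lost, 39.9 events in 950 patients give 3.09% to 5.68%.

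**2. When closure can occur.** The time points in section 4.3 are months 1, 6, 12, 24, 36, 48 and 60. Closure comes at the second of two consecutive misses, if contact attempts also fail:

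| Missed pair (months) | Closed at month | Months left to 60 |
|---|---|---|
| 1 and 6 | 6 | 54 |
| 6 and 12 | 12 | 48 |
| 12 and 24 | 24 | 36 |
| 24 and 36 | 36 | 24 |
| 36 and 48 | 48 | 12 |
| 48 and 60 | 60 | 0 |

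**3. What the text requires at closure.**

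- Contact attempts: required, but neither number nor type is stated.
- Vital-status check through relatives, general practitioner or civil records: not required in 6.4 or 6.5.
- Reopening a patient who is found again: not addressed.
- The no-further-data sentence: written for withdrawn patients. Section 6.5 lists loss and withdrawal separately, which suggests that the sentence does not cover lost patients. However, it directly follows a list that includes loss, and the same form closes both groups. A site could read it either way.

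**4. Illustration of bias.** The protocol gives no loss rate and no mortality among the lost, so both are assumptions here. Suppose that a share L of 1000 patients is lost before any event, that followed patients have 4.2% MACE at 1 year, and that a share d of the lost are undetected cardiac deaths.

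True MACE = [0.042 × (1000 − 1000L) + 1000L × d]/1000

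| L | d = 4.2% | d = 10% | d = 20% |
|---|---|---|---|
| 2% | 4.20% | 4.32% | 4.52% |
| 5% | 4.20% | 4.49% | 4.99% |
| 10% | 4.20% | 4.78% | 5.78% |

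For example, L = 5% and d = 10% give (39.9 + 5)/1000 = 4.49%.

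The reported figure depends on how lost patients are handled. Section 9.2 includes all registered patients, and section 9.4 names both Kaplan-Meier and adjusted Wald. At L = 5%:

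- Lost patients censored early: estimate 4.20%. The shortfall is (4.49 − 4.20)/4.49 = 6% at d = 10% and (4.99 − 4.20)/4.99 = 16% at d = 20%.
- Lost patients kept in the denominator as event-free: estimate 39.9/1000 = 3.99%. The shortfall is (4.49 − 3.99)/4.49 = 11% and (4.99 − 3.99)/4.99 = 20%.

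If lost patients have the same risk as the others (d = 4.2%), the censored estimate is unbiased.

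**5. Rare events.** If the 0.9% 12-month scaffold thrombosis rate quoted in the protocol's background for ABSORB EXTEND applied here, about 9 events would be expected per 1000 patients. Each missed event would then be 1/9 = 11% of the total.

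**The case against.** The strongest reply is that the rule is narrower, and its setting more protective, than it may seem.

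- **The trigger.** A reader might infer that two missed visits alone close a patient. They do not: contact attempts must also have failed, and the default in 6.4 is retention to the end of follow-up. This stands. The attempts are undefined, however, and failed contact is also what a death can produce.
- **Other sources of information.** Section 12.2 bases data collection on chart review. Section 12.1 asks for the patient's condition at completion or withdrawal, and section 11.2 has an independent committee analyse source documents for events. A relative may also report a death by telephone. So it would be wrong to say that a dead patient cannot be told apart from a silent one. None of these provisions, though, requires a site to trace a patient it cannot reach.
- **Reopening.** A reader might infer that a lost patient has no way back into the data. The documents do not support that: the explicit bar names withdrawn patients, and on lost patients the text is silent. A readmission at the implanting site is the case that chart review would most readily catch. What remains is an ambiguity.
- **Size.** A 10% to 20% cardiac death rate among the lost is 2.4 to 4.8 times the planned rate for the whole composite (10/4.2 and 20/4.2), and nothing in the protocol justifies it. A firm percentage undercount therefore cannot be claimed.
- **Cause.** A patient who has already died will not answer later calls. Dropping the two-visit rule alone would recover none of those deaths; only a status check would. This stands, and it is why the fix needs both parts.

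Tracing details could sit in the monitoring plan promised in section 11.2, which is not available here. But the closure rule is stated in the protocol, so it is best changed there.

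**Conclusion.** The concern holds in a limited form. Sections 6.4, 6.5 and 4.3 together allow discontinuation for non-response from month 6, with up to 54 of 60 months then unobserved. That follows directly from the text. No vital-status check is required first, and the status of lost patients under the no-further-data sentence is unclear.

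It is plausible, but not stated in the protocol, that some deaths would be filed as losses and that 5-year mortality, cardiac death and scaffold thrombosis would be under-ascertained. The amount cannot be derived. Under the assumed grid, true 1-year MACE ranges from 4.20% (no bias with censoring) to 5.78% (10% lost, 20% of them undetected cardiac deaths), against 4.20% in followed patients. The section 9.3 interval is arithmetically correct and unaffected. This is a design weakness worth correcting because the remedy is cheap; it is not an error in a figure.

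**What to change.** In sections 6.4 and 6.5:

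- Record a missed contact as missed, and attempt contact again at each later scheduled time point. State the number and type of attempts.
- Assign final lost-to-follow-up status, with its completion form, only at the end of the patient's planned follow-up.
- For patients who have not withdrawn consent, require a check of vital status and readmissions from site records, family or general practitioner, and the population register where consent and law allow.
- State that the no-further-data sentence applies only to withdrawn patients, so that a patient found again, or an event learned of later, is entered.

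Continued contact recovers later events in patients who are alive; the status check recovers deaths. The cost is protocol and eCRF wording, a line in the consent form, and a few extra calls per non-responder.

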12.1 Source Documentation

 Medical history/physical condition of the patient before involvement in the registry sufficient to verify protocol entry criteria

- Dated and signed notes on the day of entry into the registry referencing the sponsor, protocol number, patient ID number and a statement that informed consent was obtained
- Dated and signed notes from each patient visit
- Adverse events reported and their resolution including supporting documents such as discharge summaries, catheterization laboratory reports, ECGs, and lab results including documentation of site awareness of SAEs and of investigator device relationship assessment of AEs.
- Notes regarding Dual Anti Platelet Therapy medications taken during the registry
- (including start and stop dates)
- Patient's condition upon completion of or withdrawal from the registry
- Any other data required to substantiate data entered into the CRF

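### Section 6.4 stops all recording after a physician withdraws a patient on clinical grounds, which can lose endpoint events and can bias MACE, mortality and stent thrombosis downward

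*Protocol*

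**What the plan says.** Section 6.4 starts from retention: "each patient shall remain in the registry until completion of the required follow-up period". It then lists possible reasons for discontinuation. Next to the patient's own withdrawal and loss to follow-up stands "Patient withdrawal by physician as clinically-indicated", with no criteria for when this applies. The rule for what follows is the same for every withdrawn patient: "No additional data is needed and will be recorded from patients once withdrawn from the registry". It adds: "Patients will not be replaced".

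Section 6.5 makes the case in which "the investigator withdraws the patient from the registry" a completion event of its own, separate from the patient's own withdrawal. Section 12.1 asks the site to document "Patient's condition upon completion of or withdrawal from the registry", which describes the patient at exit and nothing later. No section provides for vital status or events after a physician withdrawal.

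Section 5 sets MACE as the primary endpoint and follows all-cause mortality, any myocardial infarction and stent thrombosis to 5 years. Section 9.2 analyses every registered patient. Section 9.4 bases inference on adjusted Wald intervals and uses Kaplan-Meier for survival analysis.

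**The concern.** Withdrawal by a physician has a clear meaning where a study assigns a treatment that may have to be stopped. Here the scaffold is already implanted, section 7 leaves treatment strategy to the investigator, and sections 4.1 and 7.4 allow follow-up by telephone. Leaving the registry therefore changes nothing but the data. Consent does not require the stop either: under section 6.2.2 the patient has agreed to data collection and follow-up, and a decision by the physician does not revoke that.

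The reason for exit is clinical by its own terms, so it may well be related to prognosis. If it is, censoring at withdrawal is informative, and standard Kaplan-Meier assumes that it is not. The outcomes exposed are the registry's main ones. The registry has a single arm (section 1), so there is no comparator in which the bias could cancel. A statistical analysis plan could describe or bound the loss, but it could not recover deaths and infarctions that were never recorded.

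**Working it through.** **1. The plan's own figure.** Section 9.3 gives a 95% adjusted Wald interval of 3.1% to 5.6% for 42 events in 1000 patients. With z = 1.96:

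- n~ = n + z² = 1003.84
- p~ = (x + z²/2)/n~ = 43.92/1003.84 = 4.375%
- half-width = z·√(p~(1 − p~)/n~) = 1.265 points
- interval: 3.11% to 5.64%

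The stated interval reproduces. The withdrawal rule does not touch this arithmetic. It bears on whether the point estimate is aimed at the right value.

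**2. Inputs for the bias.** The documents give n = 1000, the endpoints, the analysis population and the methods. They do not give a withdrawal rate, the risk of withdrawn patients or an expected 5-year MACE rate. Assumed here:

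- true 5-year MACE F = 15%
- share withdrawn by physicians w = 1% or 5%
- risk in withdrawn relative to retained patients R = 1, 2 or 3
- every withdrawal occurs early and before any event, which is the least favourable timing

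**3. Formulas.** Let F0 be the risk in retained patients. Then F = (1 − w)F0 + wR·F0, so F0 = F/(1 − w + wR). With early censoring, Kaplan-Meier estimates F0. If the denominator is all registered patients and withdrawn patients contribute no events, the crude proportion estimates (1 − w)F0.

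**4. Results at 5 years (true value 15%).**

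| w | R | Kaplan-Meier | bias (points) | Crude, all registered | bias (points) |
|---|---|---|---|---|---|
| 1% | 1 | 15.00% | 0 | 0.99 × 15.00 = 14.85% | 0.15 |
| 1% | 2 | 15/1.01 = 14.85% | 0.15 | 0.99 × 14.85 = 14.70% | 0.30 |
| 1% | 3 | 15/1.02 = 14.71% | 0.29 | 0.99 × 14.71 = 14.56% | 0.44 |
| 5% | 1 | 15.00% | 0 | 0.95 × 15.00 = 14.25% | 0.75 |
| 5% | 2 | 15/1.05 = 14.29% | 0.71 | 0.95 × 14.29 = 13.57% | 1.43 |
| 5% | 3 | 15/1.10 = 13.64% | 1.36 | 0.95 × 13.64 = 12.95% | 2.05 |

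All biases are downward. As a yardstick, the adjusted Wald half-width at 150/1000 is 1.96 × √(0.1513 × 0.8487/1003.84) = 2.2 points.

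**5. Results at 1 year (true value 4.2%, the rate assumed in section 9.3).** The same formulas give:

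- w = 1%, R = 3: Kaplan-Meier 4.2/1.02 = 4.12%, crude 4.08%
- w = 5%, R = 3: Kaplan-Meier 4.2/1.10 = 3.82%, crude 3.63%
- w = 10%, R = 5, an extreme case: Kaplan-Meier 4.2/1.40 = 3.00%, crude 2.70%. The crude 95% interval of 1.9% to 3.9% then excludes 4.2%.

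**6. What drives the result.** At R = 1 Kaplan-Meier is unbiased, so its bias depends on withdrawn patients being at higher risk. The crude proportion falls at R = 1 as well, because events after withdrawal leave the numerator while the patients stay in the denominator.

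**The case against.** A reader might infer that the rule does remove the sickest patients before their events, and so does understate the outcomes. The Protocol does not support that. Retention is the default, physician withdrawal appears only as one conceivable reason for leaving, and nothing says who would be withdrawn, how many or when. With no registry treatment to stop, physicians may have little cause to use the option, so a share near 1% is plausible, though the document does not settle it. At that share the Kaplan-Meier bias is 0.15 to 0.3 points, and even at 5% it stays inside the interval half-width.

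Timing also matters. A MACE before withdrawal is already counted, and the deterioration or repeat procedure that prompts a withdrawal may itself be an endpoint event. Documenting the patient's condition at withdrawal gives some chance of capturing it. What is lost is whatever comes later, including death.

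It would also be too broad to say that no planned model can help. A multivariable Cox model tolerates censoring that depends on covariates in the model. It does not repair withdrawal driven by unmeasured deterioration after baseline, and it does not correct the overall event rate.

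These objections limit the certainty and the size. They do not remove the fault: the rule is explicit, no other section offsets it, and the lost events cannot be recovered at analysis.

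**Conclusion.** The point holds in conditional form. Section 6.4 allows withdrawal on undefined clinical grounds and then ends all recording for patients who have not withdrawn consent. This can remove higher-risk patients and can bias MACE, all-cause mortality and stent thrombosis downward. It does not show that such a bias will occur.

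Under the stated assumptions (5-year MACE of 15%, risk ratio 2 to 3, early withdrawal before any event), the Kaplan-Meier bias is about 0.15 to 0.3 points at 1% withdrawn and 0.7 to 1.4 points at 5%. For the crude proportion over all registered patients it is about 1.4 to 2.0 points at 5%, close to the half-width of about 2.2 points. That last comparison assumes that withdrawn patients stay in the denominator. Section 9.2 suggests this but does not spell it out.

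The change should be made because it is cheap and the data cannot be recovered later. With no evidence on how often the option would be used, nothing stronger is justified.

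**What to change.** - In section 6.4, restrict the rule that no further data are recorded to patients who withdraw consent.
- For patients withdrawn by a physician, continue to ascertain vital status and endpoint events by telephone or from records, on the existing schedule and within the consent given.
- Align section 6.5, so that withdrawal by the investigator no longer closes event recording.
- Report the number of withdrawals by reason.

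Little needs adding for patients who withdraw consent. Section 6.4 stops only additional data, section 6.5 already requires a completion form, and sections 12 and 12.1 keep discontinuation information and the condition at exit.

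The cost is a wording change in the Protocol and the consent form, with the ethics committee approval that sections 11.1 and 13.1 require, and a few more contacts within the planned follow-up.

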6.5 Registry Completion

An eCRF registry completion form must be completed when:

- the patient is considered lost-to-follow-up per the above definition or
- the patient withdraws from the registry or
- the investigator withdraws the patient from the registry or
- the patient's follow-up is terminated upon registry follow-up completed (see Section 4.3 for details)

7. TREATMENT AND SCHEDULE OF EVENTS

The treatment strategy will be determined by the investigator. It is required that each enrolling investigator review the most recent Absorb BVS IFU and assess the contraindications, warnings and precaution sections with respect to the risks and benefits for treating potential patients.

7.1 Baseline

Patient preparation will be in accordance with standard hospital policy for the care of interventional cardiology patients.

Baseline data will be collected as per eCRF. The Syntax score will be calculated in all patients.

7.2 Procedure

During the procedure, patients will receive appropriate anticoagulation and other therapies according to standard hospital practice. The Absorb BVS will be inspected, prepared, and implanted according to the IFU.

QCA analysis is recommended pre implantation of the ABSORB, for correct sizing. IVUS, VH-IVUS and OCT techniques are encouraged: these imaging tools will be subject of subgroup analysis.

7.3 Post-procedure (In-hospital)

Post procedure data will be collected as per eCRF

7.3.1 Follow-up Antiplatelet Medications

A minimum of 6 months duration of DAPT is recommended. Specific type of DAPT

will be recorded as per eCRF.

7.4 Clinical Follow-up

Clinical follow-up visits by telephone contact or office visits per the following

schedule.

30 days: office visit is encouraged

6 months: office visit is encouraged

• 1 year, and then yearly up to 5 years after the index procedure: office

visit is encouraged.

7.5 Angiographic follow up

The angiographic follow up will be clinically driven. However, patients undergoing

angio follow up and IVUS or OCT follow up will be included in subgroup analysis.

8. ADJUDICATION OF EVENTS

In order to minimize bias in assessing MACE outcomes, these events will be

adjudicated by an independent Clinical Event Committee, which will also act as

Data Safety and Monitoring Board for the study.

